## 4.2 PRIMARY ENDPOINT(S)/ESTIMAND(S) ANALYSIS

### 4.2.1 Definition of Primary Estimand/Endpoints

The primary endpoint/estimand is to compare the safety of a single dose of baloxavir marboxil with 5 days of oseltamivir administered twice a day (BID), as defined in [Table 1](#).

## **4.2.2        Main Analytical Approach for Primary Estimand/Endpoints**

Safety will be assessed through summaries or listings of adverse events, clinical laboratory test results, and vital signs.

### **4.2.2.1        Adverse Events**

Only treatment-emergent adverse events (AEs) will be summarized. Treatment-emergent AEs (TEAEs) are defined as those AEs with observed or imputed onset date on or after the start date of trial treatment. Only where the most extreme intensity is greater than the initial intensity (or if most extreme intensity was not missing and initial intensity was missing) will events with an onset date prior to the start of study drug considered treatment emergent. An AE with a completely missing start date was assumed to be treatment-emergent unless the AE had a complete non-imputed end date that was prior to study Day 1.

Adverse events will be coded and tabulated by system organ class (SOC) and/or preferred term (PT). In tabulations, PTs and their associated SOC will be presented in order of descending frequency summed across the treatment groups. AEs will also be tabulated by severity.

The following will also be summarized by treatment, and listings produced where required:

- All AEs
- Serious AEs (SAEs)
- AEs related to study drug
- AEs by severity
- AEs by outcome
- AEs leading to study drug discontinuation
- AEs leading to study withdrawal
- AEs leading to death
- AEs leading to a dose modification or interruption
- Most frequent AEs
- Adverse Event of Special Interest (AESIs) as follows (based on the data reported on AE form):
  - Cases of potential drug-induced liver injury that include an elevated alanine aminotransferase (ALT) or aspartate aminotransferase (AST) in combination with either an elevated bilirubin or clinical jaundice, as defined by Hy's Law
  - Suspected transmission of an infectious agent by the study drug, as defined in protocol

If the overall number of AEs is low, then listings may be provided instead of the above summaries.

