Appendix 1: Regulatory, Ethical, and Study Oversight Considerations

Participants must be informed that their medical records may be examined by auditors or other authorized individuals representing the Sponsor or Sponsor collaborators and licensees, by appropriate IRB/EC members, and by inspectors from health authorities.

A1–5 ADMINISTRATIVE STRUCTURE

This trial will be sponsored and managed by F. Hoffmann-La Roche Ltd. The Sponsor will provide clinical operations management, data management, and medical monitoring.

Approximately 20 sites globally will participate to enroll approximately 100 participants. Enrollment will occur through an interactive voice or Web-based response system.

Central facilities will be used for certain assessments throughout the study (e.g., specified laboratory tests, biomarker and pharmacokinetic analyses), as specified in Section 8 and [Appendix 2](#). Accredited local laboratories will be used for routine monitoring; local laboratory ranges will be collected.

A1–6 DISSEMINATION OF CLINICAL STUDY DATA

Study data may be submitted to government or other health research databases or shared with researchers, government agencies, companies, or other groups that are not participating in this study. These data may be combined with or linked to other data and used for research purposes, to advance science and public health, or for analysis, development, and commercialization of products to treat and diagnose disease. In addition, redacted Clinical Study Reports and/or other *summaries of clinical study results may be available in health authority databases for public access, as required by local regulation, and will be provided upon request.* For more information, refer to the Roche Global Policy on Sharing of Clinical Study Information at the following website:

<https://www.roche.com/innovation/process/clinical-trials/data-sharing/>

A1–7 DATA QUALITY ASSURANCE

All participant data relating to the study will be recorded on electronic Case Report Forms (CRFs) unless transmitted to the Sponsor or designee electronically (e.g., laboratory data). The investigator is responsible for verifying that data entries are accurate and correct by physically or electronically signing the CRF.

The investigator must maintain accurate documentation (source data) that supports the information entered in the CRF.

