A persistent adverse event is one that extends continuously, without resolution, between participant evaluation timepoints. Such events should only be recorded once on the Adverse Event eCRF. The initial severity (intensity or grade) of the event will be recorded at the time the event is first reported. If a persistent adverse event becomes more severe, the most extreme severity should also be recorded on the Adverse Event eCRF. If the event becomes serious, it should be reported to the Sponsor immediately (i.e., no more than 24 hours after the investigator becomes aware that the event became serious; see Section [A3–5](#) for reporting instructions). The Adverse Event eCRF should be updated by changing the event from "non-serious" to "serious," providing the date that the event became serious, and completing all data fields related to serious adverse events.

A recurrent adverse event is one that resolves between participant evaluation timepoints and subsequently recurs. Each recurrence of an adverse event should be recorded as a separate event on the Adverse Event eCRF.

A3–7.4 ABNORMAL LABORATORY VALUES

Not every abnormal laboratory value qualifies as an adverse event. A laboratory value abnormality that is associated with the underlying disease should not be reported as an adverse event unless judged by the investigator to be more severe than expected.

A laboratory value abnormality that is not associated with the underlying disease must be reported as an adverse event if it meets any of the following criteria:

- Is accompanied by clinical symptoms
- Results in a change in study treatment (e.g., dose modification, treatment interruption, or treatment discontinuation)

Appendix 3: Adverse Events: Definitions and Procedures for Recording, Evaluation, Follow-Up, and Reporting

- Results in a medical intervention (e.g., potassium supplementation for hypokalemia) or a change in concomitant therapy
- Is clinically significant in the investigator's judgment

It is the investigator's responsibility to review all laboratory findings. Medical and scientific judgment should be exercised in deciding whether an isolated laboratory abnormality should be classified as an adverse event.

If a clinically significant laboratory abnormality is a sign of a disease or syndrome (e.g., ALP and bilirubin 5× upper limit of normal (ULN) associated with cholestasis), only the diagnosis (i.e., cholestasis) should be recorded on the Adverse Event eCRF.

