The finding of an elevated ALT or AST ($> 3 \times \text{ULN}$) in combination with either an elevated total bilirubin ($> 2 \times \text{ULN}$) or clinical jaundice in the absence of cholestasis or other causes of hyperbilirubinemia is considered to be an indicator of severe liver injury (as defined by Hy's Law). Therefore, investigators must report as an adverse event the occurrence of either of the following:

- Treatment-emergent ALT or AST $> 3 \times \text{ULN}$ in combination with total bilirubin $> 2 \times \text{ULN}$
- Treatment-emergent ALT or AST $> 3 \times \text{ULN}$ in combination with clinical jaundice

The most appropriate diagnosis or (if a diagnosis cannot be established) the abnormal laboratory values should be recorded on the Adverse Event eCRF (see Section [A3-7.1](#)) and reported to the Sponsor immediately (i.e., no more than 24 hours after the investigator becomes aware of the event), either as a serious adverse event or an adverse event of special interest (see Section [A3-5](#)).

A3-7.7 DEATHS

All deaths that occur during the protocol-specified adverse event reporting period (see Section [8.3.1](#)), regardless of relationship to study treatment, must be recorded on the Adverse Event eCRF and immediately reported to the Sponsor (see Section [A3-5](#)). This includes death attributed to progression of influenza.

Death should be considered an outcome and not a distinct event. The event or condition that caused or contributed to the fatal outcome should be recorded as the single medical concept on the Adverse Event eCRF. Generally, only one such event should be reported. If the cause of death is unknown and cannot be ascertained at the time of reporting, **"unexplained death"** should be recorded on the Adverse Event eCRF. If the cause of death later becomes available (e.g., after autopsy), "unexplained death" should be replaced by the established cause of death. The term **"sudden death"** should not be used unless combined with the presumed cause of death (e.g., "sudden cardiac death").

Appendix 3: Adverse Events: Definitions and Procedures for Recording, Evaluation, Follow-Up, and Reporting

If the death is attributed solely to progression of influenza, "influenza progression" should be recorded on the Adverse Event eCRF.

Deaths that occur after the adverse event reporting period should be reported as described in Section [A3-6](#).

A3-7.8 PREEXISTING MEDICAL CONDITIONS

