#### **4.2.2.3 Laboratory Data**

For each of the hematological and biochemical test parameters, summary statistics of observed and change from baseline values at each time point will be presented by treatment group for each scheduled time point. For laboratory parameters, post-dose observations on Day 1 will be classed as baseline.

Each observed value will be classified into three categories: Normal (for values within the normal range), High (for values higher than normal) and Low (for values lower than normal). The frequency of each category will be summarized by treatment group for each scheduled time point. Additionally, a shift table will present the changes from baseline at each scheduled time point.

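### Potential Hy's Law cases are counted only from the AE form, and no specified SAP output pairs transaminase with bilirubin in the same child as a cross-check

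*SAP*

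**What the plan says.** **Source of the count.** SAP 4.2.2.1 lists the adverse events of special interest under this wording: "Adverse Event of Special Interest (AESIs) as follows (based on the data reported on AE form". The liver item is a raised ALT or AST "in combination with either an elevated bilirubin or clinical jaundice, as defined by Hy's Law". The SAP gives no numeric threshold.

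**Numeric criterion.** This is in Protocol Appendix 3, A3–7.6. ALT or AST >3×ULN with total bilirubin >2×ULN or clinical jaundice, absent cholestasis or another cause of raised bilirubin, "is considered to be an indicator of severe liver injury (as defined by Hy's Law". The section continues: "Therefore, investigators must report as an adverse event the occurrence of either of the following". Two treatment-emergent combinations follow, one with bilirubin and one with jaundice. Each goes to the sponsor within 24 hours as a serious adverse event or an AESI.

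**General laboratory rule.** A3–7.4 says: "A laboratory value abnormality that is associated with the underlying disease should not be reported as an adverse event". The sentence goes on to except abnormalities that the investigator judges more severe than expected.

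**Data available.** Protocol Appendix 2 puts ALT, AST and total and direct bilirubin on one chemistry panel. A1–5 adds that "local laboratory ranges will be collected". Laboratory tests are scheduled on Day 1 post-dose and Day 6, and are optional on Days 15 and 29.

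**Laboratory analysis.** SAP 4.2.2.3 plans summary statistics of observed values and changes, plus shift tables. On categories it says: "Each observed value will be classified into three categories", namely Normal, High and Low. It makes the Day 1 post-dose sample the baseline.

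**The concern.** Safety is the primary objective, the trial is open-label at about 20 sites, and SAP 1.2.3 plans no data monitoring committee. A potential Hy's Law case is largely a laboratory finding, so most of the definition can be checked from collected data without relying on anyone's opinion. The SAP does not make that check. If a report is not made, the AESI row shows one case fewer and no specified output is built to reveal the difference. In an arm of about 67 children a single case would matter to the safety conclusion, so the row should be verifiable.

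**Working it through.** **1. The plan's own figure.** SAP Table 3 gives the probability of seeing at least one event among 67 baloxavir children: 1 − (1 − p)^67.

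| True rate p | 1% | 2% | 3% | 4% | 5% |
|---|---|---|---|---|---|
| Stated | 49% | 74% | 87% | 94% | 97% |
| Recomputed | 49.0% | 74.2% | 87.0% | 93.5% | 96.8% |

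The table reproduces. Its formula assumes that every event that occurs is counted.

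**2. Can the laboratory limb be derived?** Yes. The three analytes are on one panel and the local ranges are collected, so each value can be expressed as a multiple of ULN. The jaundice limb cannot be derived and must come from the investigator.

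**3. Would a specified output show an unreported case?** Side by side:

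| Output | Uses multiples of ULN | Pairs the tests within a child |
|---|---|---|
| AESI row (SAP 4.2.2.1) | Only through the investigator | Only through the investigator |
| Normal/High/Low table (SAP 4.2.2.3) | No | No |
| Shift table (SAP 4.2.2.3) | None stated | No |
| Summary statistics (SAP 4.2.2.3; ranges for changes in SAP Table 1) | No, but extremes are visible | No |
| Possible laboratory listings (SAP 4.2.2) | Not specified | Only if read by hand |

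Protocol 9.3.2 plans a shift table of baseline and maximum post-baseline severity grade. SAP 4.2.2.3 does not mention grades, although SAP Section 1 declares no changes to the planned analyses. As the SAP stands, 1.1×ULN and 5×ULN are both High.

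**4. How could a case stay off the form despite A3–7.6?** Besides a plain lapse, three judgements are open to an investigator who knows the assigned drug:
- whether the abnormality is associated with influenza and no more severe than expected (A3–7.4; A3–1 has the same exclusion). No text says that A3–7.6 overrides this;
- whether there is another cause of raised bilirubin (lead-in to A3–7.6);
- whether the elevation is treatment-emergent. There is no scheduled pre-dose laboratory sample. The baseline sample is drawn 0.5 to 4 hours after dosing under SAP Table 5.

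**5. Size, by assumption only.** Let s be the probability that a laboratory case reaches the AE form, independently for each case. The documents give no s.
- If exactly one laboratory case exists, P(row reads zero) = 1 − s: 5% at s = 0.95, 10% at 0.9, 20% at 0.8, 50% at 0.5.
- For the 67-child arm, P(row zero and at least one laboratory case) = (1 − ps)^67 − (1 − p)^67:

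| p (assumed) | s = 0.9 | s = 0.8 | s = 0.5 |
|---|---|---|---|
| 1% | 3.6% | 7.4% | 20.5% |
| 3% | 3.0% | 6.6% | 23.3% |

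The values of p are Table 3's generic adverse event rates, not estimates for Hy's Law. With a laboratory flag on the collected samples, s = 1 for the laboratory limb and these probabilities become 0.

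**The case against.** The strongest answer is that the protocol already closes the gap. A3–7.6 is the specific rule: "investigators must report as an adverse event the occurrence of either of the following". Its two bullets contain no exemption for influenza. A child with treatment-emergent ALT 5×ULN and bilirubin 3×ULN falls within them, and leaving that child off the form would be a protocol deviation. The site's task is also light. The tests are on one panel, mandatory at two time points, and investigators must document their review of every report. The sponsor's monitoring plans, which are not among these documents, may already reconcile laboratory data with AE forms.

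Most of this stands, and it limits the point in three ways.
- A reader might infer that A3–7.4 tells investigators to leave Hy's Law cases off the form. It does not. It has its own exception for greater-than-expected severity, and A3–7.6 imposes a separate duty. What remains is room for judgement.
- A reader might infer that a missed case would be invisible elsewhere, or would show only as High in two tables. That is too strong. Ranges in the change summaries would show a large rise, and listings are possible. What is missing is a specified output that pairs the tests.
- A reader might want the AESI derived from any post-dose sample in place of the AE-form row. That would count children already abnormal on the Day 1 sample, which the SAP calls baseline. It would also drop the treatment-emergent condition and the clinical assessment, and lose the jaundice limb.

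The objection does not show that reporting is verified anywhere in the SAP. A duty to report makes a miss less likely, but it does not detect one.

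**Conclusion.** The point holds as a gap in verification. The potential Hy's Law count rests on the AE form alone, and no specified SAP output pairs transaminase and bilirubin within a child or uses multiples of ULN, although the data to do so are collected. The row can read zero while the laboratory data contain a qualifying pair, but only after a reporting lapse or one of the judgements listed above. The documents do not support saying that it will.

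The size of the risk cannot be derived. The 5% to 50% range rests wholly on the assumed s, and the documents give no Hy's Law rate. Exact intervals do not measure it either: an upper 95% limit of 5.4% for 0/67 describes sampling error and is the same however cases are ascertained. This is a worthwhile low-cost improvement to a primary safety output, not a flaw that undermines the safety analysis.

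**What to change.** Keep the AE-form AESI row in SAP 4.2.2.1 and continue to take clinical jaundice from it. Add to SAP 4.2.2.3:

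1. A supplementary count by arm, with a listing, in the SAS, of children with ALT or AST >3×ULN and total bilirubin >2×ULN. Use the protocol's thresholds and the local ULN, on the same sample or within a stated pairing window, after the Day 1 baseline sample.
2. A separate display of children who already meet the criterion on the Day 1 sample, so that they are neither hidden nor counted as treatment-emergent.
3. Reconciliation of flagged children with the AE form before database lock.

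The cost is one short program and one listing from data already collected, plus medical review of any flagged child whose values have another explanation. No visit, procedure or clinical rule changes.

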9.3.2 Estimation Methods for the Primary Estimand/Endpoint

The primary objective for this study is to compare the safety of a single dose of baloxavir marboxil with 5 days of oseltamivir administered BID. All participants exposed to study treatment will be used for safety analyses. Participants will be analyzed according to the treatment they actually received.

Safety will be assessed through summaries of exposure to study treatment, adverse events, changes in laboratory test results, and changes in vital signs.

Study treatment exposure (such as treatment duration, total dose received) will be summarized with descriptive statistics.

All verbatim adverse event terms will be mapped to Medical Dictionary for Regulatory Activities thesaurus terms, and adverse event severity will be graded according to the National Cancer Institute Common Terminology Criteria for Adverse Events (NCI CTCAE) v5.0. All adverse events, serious adverse events, adverse events leading to death, adverse events of special interest, and adverse events leading to study treatment discontinuation that occur on or after the first dose of study treatment (i.e., treatment-emergent adverse events) will be summarized by mapped term, appropriate thesaurus level, and severity grade. For events of varying severity, the highest grade will be used in the summaries. Deaths and cause of death will be summarized.

Relevant laboratory, vital sign (pulse rate, respiratory rate, blood pressure, pulse oximetry, and temperature) will be displayed by time, with grades identified where appropriate. Additionally, a shift table of selected laboratory tests will be used to summarize the baseline and maximum post-baseline severity grade. Changes in vital signs will be summarized.

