### 1.1 TRIAL OBJECTIVES, ENDPOINTS, AND ESTIMANDS

**Table 1 Primary and Secondary Objectives and Corresponding Estimand**

Safety (Primary) Objective	Estimand Definition

To describe the safety of a single dose of baloxavir marboxil compared with 5 days of oseltamivir administered BID in Chinese pediatric participants

	

Population: All participants aged 1 to <12 years with influenza symptoms who received at least 1 dose of study treatment

Endpoint:

Incidence, severity, and timing of adverse events, serious adverse events, with severity determined according to NCI CTCAE v5

Change from baseline in vital sign measurements

Change from baseline in clinical laboratory test results

Treatment:

Experiment arm: baloxavir marboxil single dose

Control arm: oseltamivir 5 days BID

Intercurrent events and handling strategies

Treatment discontinuation: treatment policy strategy

Rescue medication: treatment policy strategy

Population-level summary:

No formal statistical testing will be conducted. Analyses will be descriptive.

Incidence of adverse events, serious adverse events by System Organ Class, by Preferred Term and by worst severity

Change from baseline summaries will be presented overall and by treatment with use of descriptive statistics, including means, standard deviations, medians, and ranges for continuous variables

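### The SAP lets listings replace by-arm adverse event summaries when the AE count is low, although AE and SAE incidence is an unconditional part of the primary estimand

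*SAP*

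**What the plan says.** SAP Table 1 gives the adverse event endpoint of the primary estimand as "Incidence, severity, and timing of adverse events, serious adverse events, with severity determined according to NCI CTCAE v5", and its population-level summary as "Incidence of adverse events, serious adverse events by System Organ Class, by Preferred Term and by worst severity". Neither depends on how many events occur. The same table lists two further primary endpoints, change from baseline in vital signs and "Change from baseline in clinical laboratory test results". SAP 4.2.1 states the purpose: "The primary endpoint/estimand is to compare the safety of a single dose of baloxavir marboxil with 5 days of oseltamivir".

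Protocol 9.3.2 says that safety is assessed through summaries, and that AEs, SAEs and the other AE categories "will be summarized by mapped term, appropriate thesaurus level, and severity grade".

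SAP 4.2.2 is looser: "Safety will be assessed through summaries or listings of adverse events, clinical laboratory test results, and vital signs". SAP 4.2.2.1 first commits to tabulating AEs by SOC and/or PT and by severity. It then gives a bulleted list of by-treatment summaries that includes all AEs, SAEs and AEs by severity. It closes with: "If the overall number of AEs is low, then listings may be provided instead of the above summaries".

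SAP section 1 says that it takes precedence over the protocol for a regulatory filing, and that the protocol's planned analyses are unchanged.

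**The concern.** The closing sentence of SAP 4.2.2.1 ties the form of a primary analysis to the outcome being analysed. The word low has no number attached, and no decision-maker or decision time is named. The count is known only once events have accrued, and the study is open-label.

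A listing is a different object from an incidence. It prints no denominator and no percentage, and it omits children who had no event. If listings are used, the measure that the estimand names may not be reported.

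The protocol wording does not close the gap, because the SAP overrides it for filing. The option is also a departure from protocol 9.3.2 that the SAP does not declare. In a descriptive trial with no hypothesis test, the by-arm incidence table is the primary AE result, so it should not be optional.

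**Working it through.** **1. The plan's own figure.** Protocol Table 8 and SAP Table 3 give the chance of seeing at least one child with an AE of true incidence p among 67 on baloxavir. The formula is 1 − (1 − p)^67. For p = 1% to 5% it gives 49.0%, 74.2%, 87.0%, 93.5% and 96.8%, against the stated 49%, 74%, 87%, 94% and 97%. All five reproduce. These figures concern one specific event, not the overall number of AEs, so they do not show how likely the listings option is to be used.

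**2. The commitments side by side.**
- SAP Table 1: incidence of AEs and SAEs by SOC, PT and worst severity. No condition.
- Protocol 9.3.2: AEs and SAEs summarised by term, thesaurus level and grade. No condition.
- SAP 4.2.2: summaries or listings.
- SAP 4.2.2.1: listings in place of summaries if the overall count is low.
- SAP section 1: no change from the protocol.

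The third and fourth items cannot both apply as written alongside the other three.

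**3. How far the sentence reaches.**
- *Wider reading.* It covers every summary above it in SAP 4.2.2.1, including the SOC/PT and severity tables. The wording of SAP 4.2.2 supports this. All by-arm AE incidence can then be left out.
- *Narrower reading.* It covers only the bulleted list, because that list is introduced as summaries while the SOC/PT and severity outputs are called tabulations. Those tabulations then stay. The bulleted list, however, holds the all-AE and SAE summaries by treatment, and SAEs appear as a category of their own only there. The SAE part of the estimand's summary can therefore still go.

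**4. What a listing shows under 2:1 allocation.** The inputs are 67 and 33 children (SAP 2.2).
- Expected ratio of listed events at equal rates: 67/33 = 2.03.
- Near-equal rates: 6/67 = 9.0% and 3/33 = 9.1%. A listing shows six against three.
- Unequal rates: 5/67 = 7.5% and 5/33 = 15.2%. A listing shows five against five, although one rate is about twice the other (15.2/7.5 = 2.03).

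The 6-, 3- and 5-event counts are illustrations. The denominators are planned numbers.

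**5. How likely the option is to be used.** The documents give neither a cutoff nor an expected AE rate, so both are assumed here. Taking children with at least one AE as a proxy for the overall count, with N = 100 and a common rate:

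| Assumed any-AE rate | P(10 or fewer children) | P(15 or fewer children) |
|---|---|---|
| 10% | 58% | 96% |
| 20% | 0.6% | 13% |
| 30% | about 0% | about 0% |

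The answer runs from almost never to almost always, depending on the rate and on a cutoff that the SAP leaves open.

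**The case against.** The case against has real force on several points.

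- **Nothing is hidden.** A listing shows every event, and SAP 4.4.1 reports exposure by arm on the safety analysis set, so the denominators will be available. With few events a reader can form n/N by hand. A listing can also show event timing, which is part of the endpoint and which a SOC/PT table does not show. This stands, but a plan should commit to its own estimand's summary and not leave the reader to build it.
- **The trigger is not comparative.** It is the overall count, not a difference between arms, and no hypothesis is tested. This also stands: there is no type I error issue and no shown mechanism that favours either arm. The weakness is an undefined choice made after data are seen.
- **Core tables may survive.** On the narrower reading the SOC/PT and severity tabulations remain. This is plausible, and it is why the wider consequence cannot be stated as certain.
- **The option may never be used.** With any-AE rates of 20% or more, a count of ten or fewer children is very unlikely.

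Three stronger readings are tempting, but the documents do not support them:

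- A reader might infer that the trial's whole primary result can be dropped. It cannot. Laboratory and vital-sign changes are also primary. SAP 4.2.2 mentions them in the same loose phrase, but SAP 4.2.2.3 and 4.2.2.4 specify their summaries without condition.
- A reader might infer that the trial was sized to show a low AE count. The documents say that no formal calculation was made, and the 87% is for a single event of 3% incidence.
- A reader might infer that exact limits, such as an upper bound of 5.4% for 0/67, would be lost. No confidence intervals for AE incidence are planned, so the tables would not give them either.

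**Conclusion.** The conflict is real and should be fixed, and its scope is limited. SAP 4.2.2 and 4.2.2.1 allow listings to replace by-arm AE summaries on an undefined trigger that can be judged only after data are seen. SAP Table 1 and protocol 9.3.2 make the incidence summary unconditional, and SAP section 1 declares no change.

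On the wider reading the AE component of the primary estimand could be reported without any by-arm incidence. On the narrower reading the all-AE and SAE summaries by treatment could still be missing. What is at risk is the printed n, N and percentage, not the events themselves, and the closing sentence of SAP 4.2.2.1 leaves the laboratory and vital-sign components alone.

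The practical size is the allocation effect: about two listed baloxavir events per oseltamivir event when rates are equal. This assumes that the planned 67 and 33 are roughly achieved and that the listing carries no denominators. How often the option would be used cannot be judged from the documents.

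**What to change.** Three wording changes in the SAP:

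1. In 4.2.2, replace the choice between summaries and listings with summaries supported by listings.
2. In 4.2.2.1, delete the closing sentence, or limit it to minor breakdowns such as AEs by outcome. If it is kept in that form, fix a numeric threshold before data review.
3. State that n and % by arm, on the safety analysis set denominator, are always produced for all AEs and for SAEs by SOC, PT and worst grade, including zero counts.

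On this point the statement in section 1 that the protocol's analyses are unchanged would then be accurate. The cost is a small wording edit and, if events are few, at most a few sparse tables. No new data, assessments or design changes are needed.
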